5.6.1. Extent of Exposure

Treatment exposure-related variables will be summarized for the VT and VRT populations. Study treatment exposure will be measured by volume injected at each treatment (Table 5-6). The number and percentage of participants for the study intervention volume injected will be tabulated by cheek at initial, touch-up, and repeat treatments as well as the combination of the initial and touch-up treatments.

Table 5-6 Exposure to Study Treatment

Endpoint	Description	Timing	Methodology
Volume injected • Left cheek • Right cheek • Total	Summary by treatment group, treatment (initial, touch-up, repeat, initial and touch-up combined), and side of face	Initial, Touch-up, Repeat, Initial and Touch-up combined	Continuous descriptive statistics

5.6.2. Administration of Study Treatment

Variables related to administration of treatment listed in [Table 5-7](#) will be summarized for the VT population by treatment group and by side of the face at the initial and the touch-up treatments, and for the VRT population by side of the face at the repeat treatment.

Table 5-7 **Administration of Study Treatment**

Endpoint	Description	Timing	Methodology
Pre-treatment Anesthesia type • Ice • Topical	Summary by treatment group, treatment (initial, touch-up or repeat)	Initial, Touch-up, Repeat	Frequency counts and percentages
Pre-treatment anesthesia duration (minutes) • Anesthesia duration is computed as injection time minus start of anesthesia administration time. Summarize by treatment group, treatment, and anesthesia type.	Summary by treatment group, treatment (initial, touch-up or repeat)	Initial, Touch-up, Repeat	Continuous descriptive statistics
Treatment administration • Planes of injection • Average spacing of injection • Needle used • Number of needles used • Device/Needle problem or malfunction	Summary by treatment group, treatment (initial or touch-up), and side of face	Initial, Touch-up, Repeat	Frequency counts and percentages

5.6.3. Adverse Events

An AE will be considered a treatment emergent adverse event (TEAE) if the AE began or worsened (increased in severity or became serious) after first administration of VOLITE for the treatment group and after the date of randomization for the control group. A TESAE is defined as an SAE that is also a TEAE. Overall summary will be provided on a per-participant level for TEAEs, treatment-related TEAEs, TESAEs, deaths, and TEAEs leading to study intervention discontinuation.

If more than one event is coded to the same PT for the same participant, the participant will be counted only once for that PT using the greatest severity for the summarizations by severity and most related occurrence for the summarizations by relationship to study intervention. If the severity of a TEAE is missing, the maximum severity will be assigned to the event for the summarization by severity. The value will be displayed as missing in the data listing. If the relationship to the study intervention is missing for a TEAE, the event will be considered related to the study intervention for the summarization. The value will be displayed as missing in the data listing.

TEAEs will be summarized by treatment group for CP using the Safety population. TEAEs will also be summarized for TP and RP using the VT and VRT populations, respectively.

The number and percentage of participants with TEAEs and the events in the following AE categories will be summarized for the above populations as described in [Table 5-8](#). For participants who received repeat treatment, their AEs reported during the first month in the initial treatment period will be summarized and presented in parallel with AEs reported during the repeat treatment period.

JUVÉDERM VOLITE™ XC

Summary tables will be provided for participants with TESAEs and participants with TEAEs leading to discontinuation if these occurred in 5 or more participants. Listings of all TEAEs, AESIs, TESAEs, TEAEs leading to discontinuation, and death will be presented.

Table 5-8 **TEAE Summaries**

Endpoint	Description	Timing	Methodology
Overall summary	Overall summary only for the following categories: 
 • TEAEs • Treatment-related TEAEs • Treatment-related TEAEs at injection site • Treatment-related TEAEs not at injection site • TESAEs • Treatment-related TESAEs • Treatment-related TESAEs at injection site • Treatment-related TESAEs not at injection site • Discontinued due to TEAE • Deaths 	CP, TP, RP	Frequency counts and percentages
TEAEs	
 • Overall summary and by SOC and PT • Overall summary and by SOC, PT, and severity 	CP, TP, RP	Frequency counts and percentages
Treatment-related TEAEs	
 • Overall summary and by SOC and PT • Overall summary and by SOC, PT, and severity • Overall summary of duration, time to onset, and outcome by severity 	CP, TP, RP	Frequency counts and percentages
TESAEs	Overall summary and by SOC and PT	CP, TP, RP	Frequency counts and percentages
TEAEs leading to discontinuation	Overall summary and by SOC and PT	CP, TP, RP	Frequency counts and percentages

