5.1. General Considerations

- The primary analysis will be performed after the database is locked and randomization schedule is released.
- To account for different timing of VOLITE treatment and comparable time frame of data collection to enhance interpretability of effectiveness and safety analyses, the statistical analyses will be performed by the study periods defined below in [Table 5-1](#). For participants randomized to the treatment group, the Treated Period (TP) is the Control Period (CP) plus the Follow-up Period; for participants randomized to the control group, the TP is the Follow-up Period composed of the delayed treatment period plus the delayed treatment follow-up period ([Figure 1-1](#)). Follow-up Period starts on the end date of CP + 1 and ends on the same day as TP.

Table 5-1 Definition of the Control, Treatment, and Repeat Treatment Periods by Randomization Group

Randomization Group	Period	Treatment Group Label	Start Date	End Date
Treatment	Control Period (CP)	VOLITE	Initial treatment date	
The end date is the date of the Month 1 assessment:
 
 • If multiple assessments fall into Month 1 window, the date of the assessment included in the Month 1 analysis will be used as end date. • For participants who exit before Month 1, the end date is study exit date. • For participants with a missing assessment at Month 1, the end date is the target day for Month 1.
	Treated Period (TP)	VOLITE	Initial treatment date	Date of repeat treatment or the study exit date, whichever is earlier
	Repeat Treatment Period (RP)	VOLITE	Repeat treatment date	Study exit date
Control	CP	Control	Randomization date	
For participants who do not receive optional treatment:
 
 • If multiple assessments fall into Month 1 window, the date of the assessment included in the Month 1 analysis will be used as end date. • For participants who exit before Month 1, the end date is study exit date. • For participants with missing assessment at Month 1, the target day for Month 1 (Day 31) will be the end date. 
For participants who receive optional treatment: the end date is the date of optional treatment.

	TP	VOLITE Post-Control	Optional treatment date	Study exit date

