6.4.2. Missing Date Imputation

Missing date will be imputed for TEAEs and medications. The missing AE dates will be imputed with year, month, and day values based on the corresponding scenarios in [Table 6-5](#) and algorithms described in [Sections 6.4.2.1](#) and [6.4.2.2](#). If the AE stop date is complete and the imputed AE start date is after the stop date, the AE start date will be re-imputed using the stop date. If the imputed AE stop date is before the start date (imputed or non-imputed start date), the start date will be the imputed stop date.

The missing medication start and stop dates will be imputed based on the algorithms described in [Sections 6.4.2.3](#) and [6.4.2.4](#). When the medication start date and stop date are both incomplete for a participant, the start date will be imputed first. If the medication stop date is complete and the imputed start date is after the stop date, the start date will be imputed using the stop date. If the imputed medication stop date is before the start date (imputed or non-imputed start date), the start date will be the imputed stop date.

Table 6-5 **Imputation Scenarios**

Scenario	Complete			Imputable
	Year	Month	Day	
1	Yes	Yes	Yes	N/A
2	Yes	Yes	—	Yes
3	Yes	—	Yes	No ^a
4	Yes	—	—	Yes
5	—	Yes	Yes	No ^a
6	—	Yes	—	No ^a
7	—	—	Yes	No ^a
8	—	—	—	Yes

^a Not allowed per database design.

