6.4.2.1. Missing/Incomplete AE Start Date

For scenario 2 from Table 6-5 (if day is missing but month and year are available), then the imputed day will be the first day of the month or the date of first study treatment (which will be the date of randomization for control group) if they have the same month and year, whichever is later (because TEAE onset is not expected prior to administration of study treatment).

For scenario 4 (if day and month are missing but year is available), then the imputed day and month will be 01 Jan or the date of first study treatment (or date of randomization for control group) if they have the same year.

For scenario 8 (if day, month and year are all missing), impute start date as the latter of randomization date or first study treatment date.

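### The control-arm TEAE rule requires onset strictly after the randomization date, but SAP 6.4.2.1 imputes some incomplete control onset dates to exactly that date

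*SAP*

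**What the plan says.** SAP 5.6.3 makes an AE treatment-emergent if its onset or worsening comes "after first administration of VOLITE for the treatment group and after the date of randomization for the control group". Worsening there means a rise in severity or a change to serious. The VOLITE anchor is an event, the injection. The control anchor is a calendar date.

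SAP 6.4.2.1 imputes incomplete AE start dates:

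- **Day missing (scenario 2):** the later of the first of the month and "the date of first study treatment (which will be the date of randomization for control group) if they have the same month and year". The reason given is "because TEAE onset is not expected prior to administration of study treatment".
- **Day and month missing (scenario 4):** "01 Jan or the date of first study treatment (or date of randomization for control group) if they have the same year".
- **Date wholly missing (scenario 8):** "impute start date as the latter of randomization date or first study treatment date".

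SAP 6.4.2 adds one exception. If the imputed start falls after a complete stop date, "the AE start date will be re-imputed using the stop date".

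In SAP 5.1, Table 5-1 gives the start of the control group's Control Period as "Randomization date". A note to Protocol Table 2-2 requires randomization and first injection on the same day in the treatment group, so the anchor day has the same meaning in both arms. Protocol 10.3.2 says that pre-treatment AEs are listed but not summarized.

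**The concern.** Two current sections of the SAP conflict. The imputation puts an uncertain control onset on the randomization date so that it is not treated as pre-existing. The TEAE definition then excludes that same date. A control AE with a complete date falling on the randomization day is excluded too, although Table 5-1 puts that day inside the Control Period. That second case needs no missing data.

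The Control Period table by treatment group is the only randomized AE comparison in the study, because controls may receive VOLITE afterwards. An AE that fails the TEAE rule leaves that table. This also runs against the rest of SAP 5.6.3, where missing severity is set to the maximum and missing relationship is set to related. Those rules keep uncertain events, whereas here a missing day can remove one.

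**Working it through.** The plan states no figure on this point, so there is none to reproduce. The check applies the date rules as written and then sizes the share of partial dates affected.

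**1. One control subject, randomized 10 May 2019 (illustrative date)**

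| AE onset as recorded | Imputed start | Strictly after 10 May? | On or after 10 May? |
|---|---|---|---|
| May 2019 | 10 May 2019 | No, not a TEAE | Yes, TEAE |
| June 2019 | 1 June 2019 | Yes, TEAE | Yes, TEAE |
| April 2019 | 1 April 2019 | No | No |

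Only the first row changes with the wording. A later month goes to its first day and still counts.

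**2. Share of day-missing control AEs affected (scenario 2)**

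Assumptions: true onset is uniform over days 1 to L after randomization, and randomization is uniform over the 365 days of 2019. L = 30, with a range of 28 to 37 from the -2/+7 day window for the control Month 1 visit (Protocol Table 2-3).

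With average month length M = 365/12 = 30.42, an onset k days after randomization falls in the same calendar month with probability about 1 − k/M, or zero once k exceeds the month. Averaging over k = 1 to L gives 1 − (L + 1)/(2M) for L up to 30.

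- L = 28: 1 − 14.5/30.42 = 0.523
- L = 30: 1 − 15.5/30.42 = 0.490
- L = 37: only lags up to 30 contribute, so (30 − 465/30.42)/37 = 14.71/37 = 0.398

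Enumerating every randomization day with true month lengths gives 0.5233, 0.4907 and 0.3979. About 49% of these AEs (range 40% to 52%) are therefore imputed to the randomization date and fail the strict rule. The remainder go to the first of a later month and count.

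**3. Share of year-only control AEs affected (scenario 4)**

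The same argument with a 365-day year gives 1 − (L + 1)/(2 × 365).

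- L = 28: 1 − 29/730 = 0.960
- L = 30: 1 − 31/730 = 0.958
- L = 37: 1 − 38/730 = 0.948

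**4. Wholly missing dates (scenario 8)**

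For an untreated control the imputed date is the randomization date, and the AE fails the strict rule. For a control treated later, the rule can be read as pointing to the optional-treatment date, so the result is not fixed by the text.

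**5. The VOLITE arm**

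The same imputation lands on the first-treatment date, and an imputed date has no time. The SAP does not say whether such a date is after the first administration.

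| How the rule is programmed | VOLITE AE on anchor date | Control AE on anchor date |
|---|---|---|
| VOLITE same-day AEs count, control rule strict | TEAE | Not a TEAE |
| Strict date comparison in both arms | Not a TEAE | Not a TEAE |
| On or after the anchor date in both arms | TEAE | TEAE |

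Under the last row, the losses in steps 2 and 3 fall to 0%.

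**The case against.** A reader might infer that these AEs vanish from the control arm only, so that the VOLITE-minus-control difference is biased upward. The documents do not establish this. It requires reading the VOLITE rule leniently and the control rule strictly. That is one possible reading, but if dates are compared strictly in both arms, VOLITE AEs dated or imputed to the injection day drop out as well.

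A reader might also infer that every partial control date is lost. That is wrong. Dates in a later month survive, a stop date can move the start, later worsening makes the AE a TEAE whatever its onset, and scenario 8 may point elsewhere for a control treated later.

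The SAP also signals its intent. SAP 6.4.2 frames the imputation as being for TEAEs, and 6.4.2.1 gives a reason that implies the events should be kept. A programmer who reads both sections may well keep them. This is a fair account of what was meant, but it does not change the definition in 5.6.3.

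Excluding same-day control AEs has some logic: AEs are collected from consent, and screening may share a day with randomization, so a same-day event may precede randomization. That stands as a reason to use recorded times where they exist. It does not justify imputing dates to a day the definition excludes.

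Finally, the AE tables are counts and percentages with no planned between-arm test, pre-treatment AEs are still listed, and a one-sided loss would make the device look worse rather than hide harm. All of this stands and limits the consequence.

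**Conclusion.** The conflict between SAP 5.6.3 and 6.4.2.1 is real and can be read from the text. Applied literally, a control AE whose start is imputed to the randomization date is not a TEAE unless it worsens later or its start is re-imputed from the stop date. A fully dated control AE on the randomization day is likewise excluded by onset, despite Table 5-1.

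A difference between arms is possible but not certain, because the SAP leaves the handling of same-day and imputed VOLITE dates open.

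The affected share is about 49% (40% to 52%) of control AEs with only the day missing, and about 96% (95% to 96%) of those with only the year known. Both figures rest on uniform onset over a 28- to 37-day period and on randomization spread evenly over a calendar year. They are shares of partial-date AEs, not of all AEs. The number of partial dates is not given and is probably small, since follow-up is about a month with AE queries at visits, so the effect on TEAE incidence cannot be computed. This is worth correcting because the correction is nearly free, not because a large distortion has been shown.

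**What to change.** In SAP 5.6.3, define a TEAE as an AE with onset or worsening on or after the date of first VOLITE treatment (treatment group) or on or after the date of randomization (control group). State there that AEs whose start is imputed to that date under 6.4.2.1 count as TEAEs in both arms. The definition then agrees with 6.4.2.1 and Table 5-1.

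The change is one phrase and one sentence. The cost is that a same-day AE that preceded the injection or randomization would count in either arm unless a recorded time or a pre-treatment flag excludes it. The SAP can say that such evidence, where available, takes precedence.

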10.2 Populations for Analyses

The analysis populations will consist of subjects as defined below:

- The ITT population includes all randomized subjects. Subjects will be summarized as randomized.
- The safety population includes all subjects who are randomized to study treatment and receive at least 1 study treatment (treatment group) and subjects who are randomized to no treatment (control group). Subjects will be summarized as treated.

The Fitzpatrick V/V safety cohort will be included in the safety population for safety analyses and excluded from the ITT population for effectiveness analyses. All data for this cohort will be listed.

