A UADE is defined in accordance with 21 CFR 812.3 as “any serious adverse effect on health or safety or any life-threatening problem or death caused by, or associated with, a device, if that effect, problem, or death was not previously identified in nature, severity, or degree of incidence in the investigational plan or application (including a supplementary plan or application), or any other unanticipated serious problem associated with a device that relates to the rights, safety, or welfare of subjects.”

Assessment of Severity

Severity is a clinical determination of the intensity of an AE. The severity assessment for a clinical AE is to be completed using the following definitions as guidelines:

Mild	A type of AE that is usually transient and may require only minimal treatment or therapeutic intervention. The event does not generally interfere with usual activities of daily living.
Moderate	A type of AE that is usually alleviated with additional specific therapeutic intervention. The event interferes with usual activities of daily living, causing discomfort but poses no significant or permanent risk of harm to the research subject.
Severe	A type of AE that interrupts usual activities of daily living, or significantly affects clinical status, or may require intensive therapeutic intervention.

An event is defined as *serious* when it meets at least one of the predefined outcomes as described in the definition of an SAE/SADE, NOT when it is rated as severe.

Relationship to Treatment

Relationship to treatment refers to a determination of the relationship (if any) between an AE and the device or treatment procedure. A causal relationship is present if the PI determines that there is a reasonable possibility that the AE may have been caused by the device or is associated with

the procedure, such as an event that can be attributed to other products, surgical techniques, or medications required specifically for the procedure. Relationship to the device or procedure must be determined by the PI and cannot be delegated to other study staff.

- **Recording AEs/ADEs and/or SAEs/SADEs** When an AE/ADE or SAE/SADE occurs, it is the responsibility of the PI to review all documentation (eg, hospital progress notes, laboratory reports, and diagnostics reports) related to the event.
- The PI will then record all relevant AE/ADE or SAE/SADE information in the CRF.

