Among the 210 participants randomized, at least 135 participants are expected to have a baseline AFLS score of 2 on both cheeks or 3 on both cheeks. The number of participants with baseline AFLS score of 0, 1, or 4 on either cheek, or 2 on one cheek and 3 on the other cheek is not expected to exceed 75. Assuming at least 65% of participants will have baseline AFLS score of 2 on both cheeks or 3 on both cheeks, 72 participants in treatment group and 36 participants in control group will provide 94.4% power to detect a difference of at least 35% in the responder rates on AFLS between the treatment groups, based on a 2-sided Fisher's exact test at the 5% level. The treatment group is assumed to have at least an 80% responder rate at Month 1, and the control group is assumed to have at most a 45% responder rate. The assumptions of responder rates are estimated from Allergan Study V12-001.

The sample size calculations used an inequality test for 2 proportions to demonstrate that the treatment group is superior to the control group.

Assuming 119 participants from the treatment group and 28 participants from the control group will be treated, a total of 147 treated participants will provide 95% power to detect an AE related to treatment with an incidence rate of 2% in the population using a 1-sided exact binomial test at the 2.5% level.

The commercial software, PASS (2008, Version 8.0.13), was used for the power calculations.

4. Populations for Analysis

The analysis populations will consist of participants as defined in Table 4-1.

Table 4-1 Analysis Populations

Population	Definition	Study Treatment Assignment
mITT	All randomized participants who have baseline assessment on the ACSS scale for both cheeks, and are not in the Fitzpatrick V/VI safety cohort (see the definition below)	As randomized
Observed Primary Endpoint	All mITT participants who have Month 1 assessment on the ACSS scale for both cheeks	As randomized
Safety	All participants who are randomized and received study intervention (VOLITE or no treatment)	As treated
VOLITE Treated (VT)	Participants randomized and received VOLITE treatment at the beginning of the Control Period, or Participants randomized and received optional VOLITE treatment after the Control Period.	As treated
VOLITE Repeat Treatment (VRT)	Participants in the VT who received VOLITE repeat treatment	As treated

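### The SAP counts a TEAE with missing relationship as treatment-related even in controls who have not been injected; the rule needs an exposure condition, though the likely effect is small

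*SAP*

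**What the plan says.** SAP 5.6.3 handles a missing causality assessment in one sentence: "If the relationship to the study intervention is missing for a TEAE, the event will be considered related to the study intervention". It adds that the data listing will still show the value as missing. No arm, period or exposure condition is attached.

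The surrounding text brings uninjected controls within reach of that sentence:

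- The TEAE definition in SAP 5.6.3 starts the clock at first VOLITE administration for the treatment group and "after the date of randomization for the control group".
- SAP Table 4-1 treats no treatment as a study intervention, so uninjected controls belong to the Safety population. Protocol 10.2 also includes them.
- SAP 5.6.3 then says: "TEAEs will be summarized by treatment group for CP using the Safety population".
- Table 5-8 lists the treatment-related rows for the Control Period (CP), including "Treatment-related TEAEs at injection site".

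Protocol Appendix 12.3 gives the meaning of the variable: "Relationship to treatment refers to a determination of the relationship (if any) between an AE and the device or treatment procedure". It also says who supplies it: "Relationship to the device or procedure must be determined by the PI and cannot be delegated to other study staff". Neither document exempts uninjected controls from the missing-value rule or sets a default relationship for them.

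**The concern.** Counting a missing relationship as related is a worst-case convention for someone who has been injected, because the device might be the cause. For a control in the no-treatment period there is no device or procedure exposure, so the imputed value is not cautious. It is known to be wrong under the protocol's own definition.

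Other parts of the plan suggest an oversight. SAP 6.4.2.1 adapts the start-date imputation to controls by substituting the randomization date for the first treatment date, but the relationship rule has no matching adaptation. Table 5-8 also asks for time to onset of treatment-related TEAEs in the CP, and an imputed control event has no injection from which to count.

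What is at stake is the treatment-related block of the CP table. There, an imputed control event offsets part of the VOLITE rate. A reader of the table sees only the percentage; the blank shows only in the listing.

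**Working it through.** **Inputs**

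- 112 + 56 evaluable participants, 20% attrition, 210 randomized at 2:1 (SAP 3).
- 119 + 28 = 147 treated participants, 2% incidence, 95% power (SAP 3, Protocol 10.1).
- Number of TEAEs with missing relationship: not given in either document. Assumed here as 1 to 5 control participants and 0 to 4 VOLITE participants.
- VOLITE treatment-related rate in the CP: not given. 10% is assumed for illustration.

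**1. The plan's own figure on related AEs.** The chance of at least one event among 147 treated participants at 2% is 1 − 0.98^147 = 0.9487. This reproduces the stated 95%. It counts treated participants only, so the missing-relationship rule does not touch it.

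**2. Arm sizes.** 168 / (1 − 0.20) = 210. At 2:1 this is 140 VOLITE and 70 control.

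**3. Effect against a rule limited to exposed participants.** Let c be the number of uninjected controls counted as related only because of a blank. The control rate rises, and the VOLITE-minus-Control contrast falls, by c/70:

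- c = 1: 1.43 points
- c = 2: 2.86 points
- c = 5: 7.14 points

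Example with a 10% VOLITE rate (14/140) and two imputed participants per arm. With the rule in both arms, the contrast is 16/140 − 2/70 = 11.43 − 2.86 = 8.57 points. With the rule in VOLITE only, it is 16/140 − 0/70 = 11.43 points.

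**4. Effect against no imputation at all.** Let v be the number of VOLITE participants newly counted as related through the rule. The contrast changes by v/140 − c/70, so it narrows only if c > v/2. At a 10% VOLITE rate:

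- v = 0, c = 1: 14/140 − 1/70 = 8.57 (narrower)
- v = 2, c = 1: 16/140 − 1/70 = 10.00 (unchanged)
- v = 4, c = 1: 18/140 − 1/70 = 11.43 (wider)

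If the per-participant missing rate m is the same in both arms and the VOLITE rate is r, the contrast becomes r + (1 − r)m − m = r(1 − m). With r = 10%, that is 9.90 at m = 1% and 9.50 at m = 5%.

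**5. Which control events are certainly unexposed.** Two date rules mean that not every event placed in a control's CP precedes injection:

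- In SAP Table 5-1, the CP of a control who takes optional treatment ends on the optional treatment date, which is also the first day of that participant's Treated Period. An event after injection that day falls on a date in both periods.
- In SAP 6.4.2.1, a control AE start date with the day missing goes to the first of the month, or to the randomization date if that is later in the same month. An event after a mid-month injection could therefore be dated before it.

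The correction therefore has to depend on what is known about timing, not on the arm label or the imputed date alone.

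**The case against.** The strongest reply is that blanks should be rare. Protocol 9.5 requires relationship to be recorded for all AEs, Appendix 12.3 makes the PI determine it, and monitors check entries for completeness. For an uninjected subject, an entry of not related is at least as natural as a blank. The eCRF is not shown, and the SAP rule speaks of missing values, not of not-applicable ones. All of this stands, and it limits the likely size.

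A second reply concerns reach. Table 5-8 plans only counts and percentages, so any VOLITE-minus-Control contrast is the reader's own subtraction. The all-cause TEAE and TESAE rows, discontinuations and deaths in the same table do not use relationship. The listing leaves imputed cases traceable. This also stands.

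Two stronger readings are tempting. A reader might infer that the rule makes the device look safer in the only randomized comparison of harm. The documents do not support that: the all-cause CP rows give an unaffected randomized comparison, and against no imputation the direction depends on the blanks in both arms. A reader might also construct a large false rate. With 10% to 20% of controls having an AE, a blank share of one quarter gives 2.5% to 5%, and a blank for every one gives 10% to 20%. Both the incidence and the blank share are assumptions, and the top of that range would require the causality requirement to fail for every control with an AE.

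None of this removes the defect: where a blank does occur in an uninjected control, the written rule yields a value that contradicts the protocol's definition.

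**Conclusion.** The point holds as a defect in the rule, with a modest expected effect. As written, a blank relationship in an uninjected control becomes a treatment-related TEAE in the CP table. The reduction of 1.43 points per such participant is certain only against a rule restricted to exposed participants, and it assumes the planned 70 controls. The total cannot be computed from the documents, because the number of blanks is unknown. Controls given VOLITE by mistake are outside the point, since safety is analysed as treated.

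It would also go too far to say that the correct related rate in the control column is always zero. An event on the optional treatment date, or one with a partial date, could follow an injection, so a blanket not-related class or a not-applicable column could hide a real device event.

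**What to change.** Amend SAP 5.6.3 to the following effect:

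1. The rule that a missing relationship counts as related applies to TEAEs with onset on or after the participant's first VOLITE injection. It also applies to TEAEs whose onset relative to that injection cannot be established because the date is partial or missing.
2. TEAEs in control participants that are known to start before any VOLITE injection, and that have a missing relationship, are not counted as treatment-related.
3. Events after injection on the optional treatment date are assigned to the Treated Period.
4. Any control event that the PI has entered as related stays in the CP table; the control column is not replaced by a not-applicable entry.
5. A footnote to the treatment-related rows gives the number of participants counted as related through imputation, by arm.

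The cost is one extra programming condition and a small date-handling rule. No additional data are needed. The second clause of item 1 keeps the conservative treatment wherever exposure is uncertain.
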